## **c. Potential Risks**

Minimal risk is anticipated with the current investigation. The psychotherapeutic intervention under investigation is consistent with the treatments recommended in the VA/DoD Clinical Care Guidelines for the treatment of PTSD and mTBI. Participants randomized to TAU will have identical opportunities for treatment as non-research patients. Regarding research risk, participants may experience anxiety and/or distress during the assessment procedure and during the course of treatment. Participants may also experience discomfort as a result of being audio recorded during the course of therapy. Participants also might not experience symptomatic relief from the intervention. Potential study participants will be informed that they may choose not to participate in the study without risk to their medical care, and that similar interventions not being evaluated in the study are available in the facility without participation in the research.

All study personnel who conduct the assessments and interventions will be qualified, trained, and closely supervised by the co-Principal Investigators (co-PIs). Participants will be provided with emergency contact numbers. All participants will be clearly informed of their right to withdraw from the study at any point without adversely impacting their routine medical, psychiatric, or psychotherapeutic care.

Safety monitoring will be performed by the study staff who conduct interviews, administer assessment questionnaires, conduct psychological and cognitive assessments, and conduct interventions. Adverse events will be reported immediately to the co-PIs, who will examine the patient and determine if any additional evaluation or treatment is needed. The co-PIs will recommend termination of participation, provide appropriate referrals, and engage in follow-up if substantial decline in functioning is observed. Referral will also be offered to non-responders and any participant who requests further treatment. The co-PIs will ensure that adverse events are properly reported to the IRB. The co-PIs will review all cumulative adverse events quarterly to determine if there are any systematic problems as the co-PIs will be ultimately responsible for all safety monitoring conducted for this study.

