**For study clinicians:** If a participant presents to his/her study clinician/Interventionist with a clinical emergency (e.g. suicidality), the study clinician should address the situation as clinically appropriate. Concerns about imminent risk should be prompted by an examination of the participant's response to item #9 on the BDI (score > 2) and/or clinical inquiry. The clinician must assess and intervene within the study treatment protocol but is not limited by the parameters of the protocol in cases of imminent risk. Instead, in such cases, clinicians should address these situations consistent with optimal standards of care including hospitalization if required (see Suicidal/Homicidal Behavior Protocol in Attachment A).

In addition, any concerns of imminent risk among participants in the CABA condition are to be immediately communicated to the site investigators ([name]. at the VAPORHCS and [name]., at the VAPSHCS), including the course of action taken. The site PIs will review such cases and determine if additional intervention is necessary. This review and/or evaluation is not required of participants in the control group as they will be receiving usual VA care and evaluation and intervention for imminent risk will follow standard VA procedures.

**For study assessors:** Study assessors should follow the Suicidal/Homicidal Behavior Protocol under the following conditions: if a participant presents with a score of 2 or higher on item 9 on the Beck Depression Inventory, or when there is other information that suggests that the person may be at risk. Assessors must also contact the site investigators who will determine if additional intervention is necessary; this review and/or evaluation is not required of participants in the control group as they will be receiving usual VA care and evaluation and intervention for imminent risk will follow standard VA procedures. Participants may be connected via a "warm transfer" with the National Veterans Crisis Line or be instructed to go to their nearest medical facility's emergency department.

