**DATA SAFETY MONITORING:** Safety monitoring analyses will occur every six months from study inception through completion. The unblinded data manager will provide the blinded study statistician with a limited data set containing blinded group membership data, i.e., group membership that is numerically labeled but unidentifiable as treatment vs. control group. This dataset will also contain in-progress data safety variables including CAPS scores and any serious adverse events including 1) the onset of imminent risk of harm to self or others such as active thoughts of suicide or violence with expressed plan and intent to act; 2) the onset of psychotic and or manic symptoms; 3) a decline in global daily functioning indicating that inpatient mental health services are required for stabilization; 4) the onset or exacerbation of major medical illness that interferes with participation in regular outpatient mental health services. Differences between the treatment and control groups will be analyzed using t-test comparisons. We will consult with the CIRB and consider the appropriateness of study suspension if, at the set data monitoring time periods every six months, we find that either group of participants is experiencing, on average, an increase in CAPS scores of 12 or more points and/or is experiencing, on average significantly more SAE's including those defined above. For serious adverse events, significance is defined as a statistically significant difference of  $p < .01$  and/or a large effect size equivalent to a Cohen's  $d$  value of .8 or greater. The two study PIs will be responsible for notifying and consulting the CIRB of any conditions meeting criteria for possible study suspension within one business day of discovery.

Randomization procedures as well as overall multisite study interim, data safety monitoring and final data analyses will be conducted by our contracted statistician, [name] who is affiliated with University of California, San Diego. [name] will receive a limited data set copied in encrypted format onto CD's sent via secure FedEx with tracking services. This data set will be considered a limited data set due to inclusion of patient assessment dates and otherwise is de-identified. A Data Use Agreement will be pursued between the VAPORHCS and [name] recognizing the agreement of the terms for use of this data which shall be transmitted and accessed strictly for data analysis purposes pursuant to the goals of this study.

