**Exploratory Investigation to Provide Guidance for Future Research Directions:**

Guidance for future research will be obtained through exploratory analyses including possible mediator and moderator variables in addition to secondary outcome variables, including measures of neuropsychological test performance and general functioning. We will also investigate whether CABA-associated treatment gains are maintained over a 6 month follow-up period. The effect of moderator and mediator variables will be explored following the procedures recommended by Kraemer, Cohen and Cohen and Busemeyer and Jones.

**Anticipated time table:** Table 4 depicts a four-year study plan with 6 months for start-up and 6 months termination; 156 weeks for enrollment and 6 month follow up assessments. The study will be fully enrolled within 39 months of the start of funding of the trial. The last group of subjects will exit by month 42.

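### The SAE suspension trigger has no between-arm criterion for psychiatric SAEs alone, so balanced medical events can dilute a moderate-to-large CABA excess; one added test is a cheap, optional improvement

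*Combined protocol and SAP*

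**What the plan says.** Section 5.6 (Data Safety Monitoring) states: "Safety monitoring analyses will occur every six months from study inception through completion". The safety file carries CAPS scores and SAEs. Four SAE types are named: (1) imminent risk of harm to self or others, (2) onset of psychotic or manic symptoms, (3) decline requiring inpatient mental health care, and (4) "the onset or exacerbation of major medical illness that interferes with participation in regular outpatient mental health services". On method it says: "Differences between the treatment and control groups will be analyzed using t-test comparisons".

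Two group-level findings prompt consultation with the CIRB about suspension. One is a mean CAPS increase of 12 or more points in either group. The other is that either group "is experiencing, on average significantly more SAE's including those defined above", with significance defined as p < .01 and/or a Cohen's d of .8 or more.

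Other layers exist. Under Potential Risks: "The co-PIs will review all cumulative adverse events quarterly to determine if there are any systematic problems". Under Protection Against Risk, SAEs go to the co-PIs and the CIRB (repeated in section 6.0), and "any concerns of imminent risk among participants in the CABA condition are to be immediately communicated to the site investigators".

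**The concern.** Types 1 to 3 are the harms most plausibly linked to a psychotherapy whose participants are asked to refrain from other mental health treatment for three and a half months. Type 4 is medical. If medical events occur about equally in both arms, counting them with the psychiatric events adds variance but no difference, so a real psychiatric imbalance has to be larger to reach p < .01.

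Nothing else in the plan supplies a numeric between-arm check on psychiatric SAEs. The CAPS trigger concerns mean symptom scores. The quarterly review has no numeric criterion. Case reporting does not compare arms, and the immediate site-investigator review of imminent risk is not required for controls.

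At stake is the sensitivity of one safety trigger. No efficacy conclusion depends on it.

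**Working it through.** **Inputs from the documents.** 96 per arm; looks every six months; p < .01 or d ≥ .8; t-test. The timetable gives 6 months of start-up, then: "The study will be fully enrolled within 39 months of the start of funding of the trial" and "The last group of subjects will exit by month 42". The plan states no detection probabilities for this trigger, so there is no figure of its own to reproduce.

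**Assumptions.** All SAE rates. Even accrual over 39 − 6 = 33 months, so arm size at month m is 96 × (m − 6)/33. That gives about 17, 35, 52, 70 and 87 per arm at months 12, 18, 24, 30 and 36, and 96 at month 42. Everyone enrolled is counted at full risk. Each participant is scored 0/1 for any SAE. Medical events are independent of psychiatric ones, so P(any) = 1 − (1 − psychiatric)(1 − medical). The test is two-sided, and detection counts only a CABA excess.

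**Formulas.** With n per arm and proportions a and b: s² = [a(1 − a) + b(1 − b)]/2 × n/(n − 1); d = (a − b)/s; t = d√(n/2) on 2n − 2 df.

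**Worked example, 70 per arm (about month 30).**
- Psychiatric only, 10 v 1: a − b = .1286, s = .2632, d = .489, t = 2.89, p = .0045. The rule fires.
- One medical-only participant added per arm, 11 v 2: d = .451, p = .0085. It still fires.
- Two added per arm, 12 v 3: a − b is still .1286, s = .3047, d = .422, t = 2.50, p = .0137. It does not fire.

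**Why.** For 15% v 3% with medical events at 5%, the any-SAE risks are 1 − .85 × .95 = 19.25% and 1 − .97 × .95 = 7.85%. The difference barely moves (12 to 11.4 points), but s rises from about .28 to .34, so d drops from about .43 to .34.

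**Chance of a flag at a look**, by exact enumeration over two binomials:

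| Psychiatric risk, CABA v TAU | Per arm | Psychiatric alone | Pooled, medical 2% | Pooled, medical 5% |
|---|---|---|---|---|
| 15% v 3% | 35 | 18% | 14% | 10% |
| | 52 | 31% | 24% | 18% |
| | 70 | 49% | 38% | 27% |
| | 96 | 68% | 54% | 40% |
| 8% v 3% | 52 | 3.2% | 3.4% | 3.1% |
| | 70 | 7.3% | 6.1% | 4.6% |
| 5% v 1% | 52 | 0.9% | 1.7% | 2.1% |
| | 70 | 3.3% | 4.1% | 3.6% |
| | 96 | 9.9% | 8.2% | 5.3% |

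**If medical events are not balanced** (15% v 3%, 70 per arm, 49% alone), pooled flagging is 39% with medical events at 6% v 4% (CABA v TAU), 17% at 4% v 6%, and 53% at 7% v 3%. In the last case the dilution has gone.

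**If events are counted instead of participants** (Poisson, 15% v 3%, 70 per arm, medical 5%), simulation gives about 41% alone and 23% pooled. The direction is the same; the percentages differ.

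**With a psychiatric test added at p < .01** (medical 5%), the chance that either test fires at a look rises from 18% to 35% (52 per arm), 27% to 52% (70) and 40% to 70% (96) for 15% v 3%. For 8% v 3% it rises from 3% to 5% (52) and from 6% to 16% (96). Cumulatively through month 30 it rises from 33% to 57% (15% v 3%), 7% to 13% (8% v 3%), 5% to 8% (5% v 1%) and 3.6% to 4.4% (4% v 1%).

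**False triggers with equal arms** (psychiatric 2–15%, medical 2–10%). The added test costs at most 0.8 points per look; at 70 per arm with both rates at 10%, the chance goes from about 1.0% to 1.7%. Over six looks it adds 0.1 to 1.9 points: 1.0% to 1.1% at 2% and 2%, 3.1% to 4.2% at 5% and 5%, and 4.5% to 6.4% at 10% and 10%.

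**The case against.** The strongest reply is that the text is ambiguous. It speaks of comparisons in the plural, does not say the four types are collapsed into one indicator, and its reference to groups averaging more SAEs could mean events per participant. Tests by type would fit. This stands as a limit: if separate tests are intended, a clarifying sentence would do. Even so, no threshold is tied to any single type.

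Next, the larger losses need rates that nothing in the documents supports. A fivefold excess over about 14 weeks is a lot in a population that excludes active suicidal intent and current bipolar or psychotic disorder, and the plan anticipates minimal risk. At low rates pooling costs nothing until the last looks, and both versions of the trigger are weak. This also stands, and it is why the change is optional. Counting everyone at full risk ignores partial exposure of recent enrollees and the 15% dropout assumed for power, so the effective arm sizes are somewhat overstated.

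Finally, there is other cover: the mean-CAPS trigger, the quarterly review, immediate reporting of SAEs, and review of imminent risk in CABA. A reader might infer that psychiatric harm would go unnoticed. The documents do not support that, because these layers could well pick up clustered events. What they lack is a between-arm SAE criterion.

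**Conclusion.** The gap is real but narrow. On its natural reading, the trigger makes one comparison of all SAEs and sets no criterion for the psychiatric types alone. If medical events are about balanced, a moderate-to-large CABA excess is less likely to be flagged from about 30 per arm upward: for 15% v 3% with medical events at 5%, 18% becomes 10% at 35 per arm and 49% becomes 27% at 70. At rates such as 5% v 1%, pooling is neutral or slightly helpful up to about 70 per arm and lowers flagging only at the last looks. By the final one, at month 42, suspension has little left to protect. If medical events are themselves clearly higher in CABA, the dilution disappears.

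Two stronger readings should be resisted. Counting all SAEs is not an error; it is a normal choice and should stay. Nor does pooling always hurt, as the low-rate and unbalanced cases show. All percentages rest on assumed rates, 0/1 indicators and full exposure. They show direction and rough size, and are not forecasts for this trial.

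**What to change.** In the Data Safety Monitoring text:

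1. Leave the all-SAE rule as it is, and state that it compares all SAEs together.
2. Make sure the six-monthly safety file records each SAE's type (1 to 4, or other).
3. Add one t-test on the proportion of participants with any type 1 to 3 event, at p < .01 only. Do not carry over d ≥ .8: in small groups it is reached easily by chance, and from 23 per arm it already implies p < .01 (d = .8 gives p = .0112 at 22 per arm and .0095 at 23).
4. Let either result lead to the existing CIRB consultation.

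The cost is a sentence or two, a type code per SAE and one more t-test on a file already being prepared. Detection cannot fall, because the present rule remains. The price is up to about 0.8 points more false triggers per look and up to about 2 points over six looks, each leading only to a consultation. If SAE rates turn out low, the gain will be small.

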## 5.5 Study Evaluations

### **Visit schedules**

#### **Pre-enrollment screening:**

- 1) Medical Record Review: Study personnel will review each participant's medical record, including their neuropsychological assessment records, to document severity and type of current cognitive status, medical and psychiatric history, current treatment, and medications.
- 2) Clinical Screening Phone Interview: Study personnel will conduct a brief phone screening to ensure subjects meet initial eligibility criteria. Participants interested in the study will be asked to provide an email address for scheduling video telehealth appointments.

**Study Enrollment:** All eligible participants will complete a consent visit including:

Informed Consent: Study personnel will complete consent procedures. All effort will be made to ensure participants fully comprehend study procedures, risks, and benefits.

**Baseline Assessment:** All eligible participants will complete a baseline assessment visit including:

Baseline Psychological and Cognitive Assessment Battery (see below). This includes assessment of exclusionary diagnoses as well a brief neuropsychological battery, diagnostic interviews, and self-report questionnaires of current emotional and post-concussive symptoms. If an individual is found not be eligible during this assessment, the assessment will be discontinued at that point.

**Treatment Visits:** All eligible patients will be randomized (CABA or TAU). CABA participants will be assigned to a therapist and receive the 10-session intervention (during COVID-19 this will be completed using telehealth modalities); TAU participants will be referred to PTSD specialty care.

**Mid-treatment Assessment:** Participants will complete questionnaires at mid-treatment (approximately 7 weeks after initiation of treatment) designed to assess current emotional and post-concussive symptoms.

**Post-treatment Assessment:** Participants will complete a brief cognitive assessment battery, diagnostic interviews, and questionnaires designed to assess current emotional and post-concussive symptoms (see section B “Data Collection and Assessment” below for a list and description of each battery measure). This will take place approximately 14 weeks after the initiation of treatment.

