**Table 3: Visit and Assessment Schedule (updated for telehealth visits)**

	Visit 1, Wk. 0	Visits 2-6	Visit 7, Wk. 7	Visits 8-12	Visit 13, Wk. 14
Duration	180 mins	90 mins	60 mins	90 mins	180 mins
Purpose	screen + baseline	intervention	mid-assessment	intervention	post-assessment
Informed Consent	x				
Demographic	x				
CAPS-V	x				x
PCL-5	x		x		x
DoD HTEC	x				
NSI	x		x		x
BDI-II	x		x		x
MINI – M,H,&P	x				
MINI – MDD & SUD	x				
SLS	x		x		x
CSQ					x
NP Battery	x				x

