Power calculations can be made for repeated measures designs under specified assumptions. Hedeker et al. extend Diggle et al.'s method for various covariance structures. Procedures described by Hedeker et al. for Random Regression Models were used for the proposed study to estimate needed sample size using RMASS (see Hedeker <http://tigger.uic.edu/~hedeker/ml.html>). Data from our previous studies were used to calculate effect sizes. The design consists of a 2 (sites) X 2 (CABA vs TAU) X 4 (baseline, 7, and 14 weeks) where the slope is the dependent measure. Site and Treatment by Site interaction were included as "nuisance parameters", that is, included to account for possible overall site effects (Site) or possible site differences in treatment effects (Treatments X Site). With a balanced design (equal numbers at each site in each group), ignoring these would not increase the probability of Type I error, but would increase the Error Sum of Squares (SS) and probability of Type II error. The main effect of treatment represents the common effect size across sites if there is one, or the average site effect, if there is heterogeneity across sites. This is true because sample sizes will be balanced across treatment groups and sites. In any case, the analysis procedures will include site and site interaction effects to avoid allowing site effects to bias treatment comparisons. However, if we detect imbalances between the treatment groups within each site, we will follow the primary analyses with subsequent analyses considering the imbalances to verify that conclusions are not affected by imbalances.

Other assumptions needed are number of repeated measures, alpha-level, nature of the hypothesis (one- or two-sided), drop-out rate, and variance-covariance matrix of the longitudinal data. We assume an overall Type-I error levels alpha of .01 to .02, drop-out rate of 15%, and autoregressive covariance structure, with correlation between sequential assessments set at 0.45. Autoregressive covariance structures assume points closer together in time are more correlated than points further in time, which is more plausible compared to the equal correlation between all pair of assessments regardless of time separation assumed by the compound symmetry design. *When multiple analyses are conducted for a given hypothesis, Type I error rates will be controlled*

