*by a Westfall-Young procedure, we would include an alpha level of .04 for Hypothesis 1a, .03 for Hypothesis 1b and 2a, and .05 for Hypothesis 2b.* We estimate that with the proposed sample size of 192 (15% drop-out) patients (96 for each of the two groups), the study will have minimum power of 80% to yield a statistically significant result for a medium effect size. Hedker et al. defined medium effect size in this model as a between-group difference increasing linearly from 0 at baseline to .5 SD units at the last time point. Hypothesis 2b is a cross-sectional hypothesis using data collected only in the week 14 of the study. The proposed sample size will provided us with a minimum power of 90% to detect a medium to large effect size. The former and foundational Behavioral Activation for PTSD study by [name] and [name] yielded the following rates which also informed our proposed sample size determination: 192 screened, 81 enrolled, 10 dropped (12.3% dropout rate), 101 screen failures.

**Outcome analyses:** Data analyses will proceed in stages. Descriptive statistics and exploratory graphing such as frequencies, means, standard deviations, stem and leaf diagrams, and scatterplots will be used to assess normality of data in terms of presence of skew and/or outliers. Continuous outcome data will be transformed if necessary using an appropriate transformation such as the log transform for skewed long tailed data. Prior experience with this kind of data leads us to expect that for all variables, the distributions will be skewed and the variances not homogeneous. Similarly, potential covariates will be summarized with descriptive statistics and graphs to determine the most appropriate way to treat these variables (e.g., continuous, categorical, or interval representation). For outcome measures acquired at baseline, 7, and 14 weeks, the analytical approach will address the nature of the outcome, as well as accommodate the within

individual variability due to the repeated assessments. Results from will be inspected for bias due to drop-outs or missing data.

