**Hypothesis 1a)** PTSD symptom severity. Dependent variables: CAPS-V and PCL-5.

**Hypothesis 1b)** Functional impairment. Dependent variables: HVLTR, WAIS-IV (Digit Span subtest), DKEFS (Trails subtest), and COWAT (Verbal Fluency).

Independent variables: Treatment group (2 levels, CABA and TAU), & Time (3 levels, Weeks 0, 7, and 14). Statistical Analysis: We will analyze data on all randomized subjects in whom we have a baseline assessment and at least one post-baseline evaluation by Mixed effects model methods. Preliminary inspection of data will determine whether the outcome is nearly normal, or whether an appropriate transformation is required, or whether a generalized linear mixed model should be considered. The mixed effects model method provides an estimate of the individual variability around the population trend, the variability of the individual intercepts (baseline values) and slopes (changes across time), and the correlation between them. A fully saturated treatment by time model will be utilized for inference. Covariance structure will be chosen based on Akaike's Information Criterion (AIC). Random group level treatment effects will also be evaluated for importance based on the model AIC. This allows for any group level effects to be incorporated into the model. Denominator degrees of freedom will be calculated using the Kenward-Roger small sample correction. The design is a 2 (sites) X 2 (CABA vs TAU) X 3 (baseline, 7, and 14 weeks). The interaction of Site and Treatment X Site will be included and tested as

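### The stated minimum power of 80% for hypotheses 1a, 1b and 2a does not follow from the inputs the plan gives, and the alpha and visit count behind it are stated inconsistently

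*Combined protocol and SAP*

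**What the plan says.** Section 5.6, under Sample size and power, bases power on a random regression slope. It takes 96 per arm, a between-group difference growing linearly from 0 at baseline to 0.5 SD at the last visit, and an autoregressive structure "with correlation between sequential assessments set at 0.45". On error rate and loss it says: "We assume an overall Type-I error levels alpha of .01 to .02, drop-out rate of 15%, and autoregressive covariance structure". The same subsection then says "we would include an alpha level of .04 for Hypothesis 1a, .03 for Hypothesis 1b and 2a, and .05 for Hypothesis 2b", and concludes that "the study will have minimum power of 80% to yield a statistically significant result for a medium effect size". It lists sidedness among the assumptions needed but never gives it.

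The power text describes the time factor as "X 4 (baseline, 7, and 14 weeks) where the slope is the dependent measure". The analysis text under hypotheses 1a and 1b says "The design is a 2 (sites) X 2 (CABA vs TAU) X 3 (baseline, 7, and 14 weeks". It infers from a saturated treatment-by-time model, restricted to subjects with a baseline and at least one later value. It expects drop-out, below 15%, to fall before the first post-baseline evaluation.

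Not every outcome has three visits. Section 5.5 says "Participants will complete questionnaires at mid-treatment (approximately 7 weeks after initiation of treatment", and Table 3 ("Visit and Assessment Schedule (updated for telehealth visits") puts PCL-5, NSI, BDI-II and SLS at weeks 0, 7 and 14, but CAPS-V and the neuropsychological battery only at weeks 0 and 14.

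**The concern.** The section gives nearly enough to recompute its own power figure, and the recomputed figure is lower. If the equal-SD calculation below applies, the chance of missing a true 0.5 SD difference on a three-visit outcome is about 29-36% at alphas .04 and .03, not the 20% that the claim implies. A null PCL-5 or BDI-II result would then be read as coming from a stronger test than was run. Because the SD unit, sidedness, baseline handling and effective alpha are missing or contradictory, a reader cannot check the claim either way.

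**Working it through.** **Inputs from section 5.6.** 96 per arm; 15% loss, so 96 × 0.85 = 81.6 per arm analysed; AR(1) with .45 per seven-week step, so the week 0-14 correlation is .45² = .2025; difference 0, 0.25, 0.5 SD at weeks 0, 7, 14.

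**Assumptions, because the plan is silent.** Equal SD at all visits, two-sided test, separate baseline mean per arm.

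**Formula.** Power = Φ(0.5/SE − z), with z = 2.054, 2.170, 2.326, 2.576 for two-sided alpha .04, .03, .02, .01. With complete data on the analysed subjects, the slope test and the week-14 contrast of the saturated model have the same SE: √[4(1 − .2025)/n].

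**Attempt to reproduce 80%: three-visit outcomes**

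| Drop-out | SE | .04 | .03 | .02 | .01 |
|---|---|---|---|---|---|
| Before first post-baseline visit (n = 81.6) | √(3.19/81.6) = 0.1977 | 68.3% | 64.0% | 58.0% | 48.1% |
| Spread (96, 88.8, 81.6 at weeks 0, 7, 14), from the GLS information matrix | 0.1909 | 71.4% | 67.3% | 61.5% | 51.7% |
| None (n = 96) | √(3.19/96) = 0.1823 | 75.5% | 71.7% | 66.1% | 56.6% |

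A one-sided test with drop-out gives 78-81% at .04 and 74-77% at .03.

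**Two-visit outcomes (CAPS-V, cognitive tests), n = 81.6.** SE = √[4(1 − r)/81.6].
- r = .2025: SE 0.1977, so 68% at .04 and 64% at .03.
- r = .45: SE = √(2.2/81.6) = 0.1642, so 84% and 81%, but 76% at .02 and 68% at .01.

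The plan does not say which correlation applies to visits 14 weeks apart.

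**Dependence on the SD unit.** Table 1 (the earlier Behavioral Activation trial) shows SDs rising from pre to post. Pooling the arms by root mean square:
- PCL 8.16/12.95, ratio .630
- CAPS 15.27/25.86, ratio .591
- BDI-II 7.62/10.61, ratio .718

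With the week-14 SD as unit and ratio k, the free-baseline contrast has SE = √[2(1 + k² − 2 × .2025k)/81.6].
- PCL: SE 0.1673, so 82.5% at .04; up to 86% as a slope with drop-out spread and the week-7 SD at the midpoint (assumptions).
- CAPS: SE 0.1649, so 83.6% at .04; up to 88% on that same slope, which needs a week-7 value that Table 3 does not schedule.
- BDI-II: SE 0.1733, so 76.3% at .03; up to 80%.
- At .01 to .02 these three outcomes run from about 62% to 81%.

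With the baseline SD as unit, the PCL effect is 0.5 × .630 = 0.315 week-14 SDs. Then 0.315/0.1673 = 1.88, and power at .04 is about 43% (up to 47% as a slope with spread drop-out).

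**Alpha.** The range .01 to .02, labelled overall, lies below every level then assigned (.04, .03, .03, .05). It would fit a per-outcome share: .04/2 = .02 for the two outcomes of 1a, and .03/3 = .01 for the three of 2a. It also fits 1b if Trails is not counted: four tests are listed, but section 5.5 says Trails is not given by telehealth, which leaves three.

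**Visit count.** Four levels are stated and three named; the analysis text says three. The fourth may be left over from the six-month follow-up, which section 3.0 says is discontinued under telehealth.

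**The case against.** The strongest reply is that equal SDs are an assumption the documents argue against. The Outcome analyses paragraph expects unequal variances, Table 1 shows them, and the effect is defined in SD units at the last time point. On that reading PCL and CAPS pass 80% at .04 with no change to the test. This stands, and it makes the result conditional. It does not rescue a minimum across three hypotheses: BDI-II, a 2a outcome, reaches only 76-80% at .03, and at .01 to .02 the outcomes fall mostly short.

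The second reply is that no single test is described. The power text argues from equal baselines under randomisation, which could mean a common baseline mean, and that would exceed 80% at .02 to .04. But no passage specifies such a model, and the remark can equally be an expectation about randomised groups. Compound symmetry at .45 would give 84% at .04 and 81% at .03, but the plan calls the autoregressive form more plausible. Which of these, if any, lay behind the original software run cannot be known from the documents.

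Third, the alpha conflict may be only a wrong label, and the fourth visit only a leftover. Both are plausible, and both still need correcting.

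A reader might infer that the trial is certainly underpowered or must enrol more. The documents do not support that: several admissible readings exceed 80%.

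**Conclusion.** The 80% minimum is not supported by the test and inputs described. Under equal SDs, a two-sided test and separate baselines, a three-visit outcome has 68-71% power at .04, 64-67% at .03 and 48-62% at .01 to .02; even with no drop-out it has only 76% and 72% at .04 and .03. Two-visit outcomes lie on either side of 80% at .04 and .03, depending on an unstated correlation. The SD unit alone moves PCL at .04 from 43-47% to 82-86%. The arithmetic is firm given these assumptions; the assumptions themselves are not in the plan, so the finding is an unsupported figure and not a demonstrated shortfall. The differing alphas likewise show that the power basis is unclear. They do not show that the trial's error rate is inflated. This should be fixed before unblinding.

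**What to change.** 1. Re-run and restate power separately for three-visit outcomes (PCL-5, BDI-II, NSI, SLS) and two-visit outcomes (CAPS-V, cognitive tests). State sidedness, SD unit and variance pattern, week 0-14 correlation, drop-out pattern, per-outcome alpha, and the number of outcomes in each hypothesis under the telehealth battery. Correct the four-level time factor to three, and correct the label on the .01 to .02 range.

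2. Before unblinding, fit a common baseline mean across arms (or baseline as a covariate) and name the week-14 CABA-TAU difference as the single 1-df contrast. If a common baseline is already intended, say so. Under equal SDs and drop-out before the first post-baseline visit, SE = √[2(1 − r²)/81.6]:
   - Three-visit outcomes (r = .2025): SE 0.1533, power 88.6/86.2/82.5/75.3% at .04/.03/.02/.01.
   - Two-visit outcomes with r = .45: SE 0.1398, power 93.6/92.0/89.4/84.1%.

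Three-visit outcomes at .01 would still fall short of 80%, and the restated text should say so if that is the effective alpha.

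The cost is one power re-run and one change to the analysis plan, with no extra patients or data.
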